5.7.5. Physical Exams

Shift tables based on baseline normal/abnormal status will be provided for assessments of each physical exam category and presented by visit.

5.7.6. Spirometry and Peak Expiratory Flow (PEF)

Summaries of spirometry and PEF variables at visits without DBPCFCs performed will include:

- Descriptive statistics of spirometry and PEF variables and change from baseline by visit will be presented
- Spaghetti plots of spirometry and PEF data will be displayed by visit

Listing of spirometry and PEV data will be provided with flag indicating the status of impact by COVID-19 pandemic.

In addition, summaries of spirometry and PEF will be performed for subjects who were impacted by COVID-19 pandemic and not impacted by COVID-19 pandemic in each study period, respectively. The summaries will be performed for pre-, during, and post-COVID-19 periods for subjects impacted by COVID-19, if applicable.

5.8. Analysis of Pharmacokinetic Data

The following analyses will be conducted:

- Descriptive statistics of functional dupilumab concentrations in serum at each sampling time by dose
- Graphical presentations of median and mean (+/- SD) functional dupilumab concentration in serum vs nominal time profiles
- Graphical presentations of individual functional dupilumab concentration in serum vs actual sampling time profiles
- Assessment of the impact of anti-drug antibodies on functional dupilumab concentrations in serum

No formal statistical analysis will be performed. For the descriptive statistical analysis, concentrations below the lower limit of quantitation (LLOQ) will be set to zero. When plotted on semi-log scale, concentrations are imputed as LLOQ/2. Mean data are presented by nominal time. Individual concentrations are presented by actual time

5.9. Analysis of Immunogenicity Data

5.9.1. Analysis of ADA Data

The immunogenicity variables described in Section 4.8 will be summarized using descriptive statistics. Immunogenicity will be characterized by ADA responses and titers observed in subjects in the ADA analysis set.

The following will be summarized by treatment group and ADA titer level:

- Number (n) and percent (%) of ADA-negative subjects (pre-existing immunoreactivity or negative in the dupilumab ADA assay at all time points)
- Number (n) and percent (%) of treatment-emergent ADA-positive subjects
 - Number (n) and percent (%) of persistent treatment-emergent ADA positive subjects
 - Number (n) and percent (%) of indeterminate treatment-emergent ADA positive subjects
 - Number (n) and percent (%) of transient treatment-emergent ADA positive subjects
- Number (n) and percent (%) of treatment-boosted ADA-positive subjects

Listing of all ADA titer levels will be provided for subjects with pre-existing, treatment-emergent and treatment-boosted ADA response.

5.9.2. Analysis of Neutralizing Antibodies (NAb) Data

The absolute occurrence (n) and percent of subjects (%) with NAb positive or negative status will be provided by treatment group for subjects in the NAb analysis set.

5.10. Association of Immunogenicity with Exposure, Safety and Efficacy

5.10.1. Immunogenicity and Exposure

Potential associations between immunogenicity variables and systemic exposure to dupilumab will be explored. Plots of individual dupilumab concentration may be provided for analyzing the potential impact of treatment-emergent ADA responses, titer (high, moderate or low) and NAb on PK profiles.

5.10.2. Immunogenicity and Safety and Efficacy

Potential association between immunogenicity variables and safety may be explored with a primary focus on the following safety events during the TEAE period:

- Injection site reaction (serious or severe and lasting 24 hours or longer)
- Hypersensitivity (SMQ: Hypersensitivity [Narrow])
- Anaphylaxis (SMQ: Anaphylaxis [Narrow])

Potential association between immunogenicity variables and primary efficacy endpoints may be explored (e.g. scatter plot or spaghetti plot).

The safety and efficacy analyses mentioned above will be conducted using the following ADA response categories:

• ADA positive subjects, that is subjects with treatment-emergent or treatment-boosted response.

- ADA negative subjects, that is subjects with pre-existing immunoreactivity or negative in the ADA assay at all time points
- Subjects with persistent treatment-emergent ADA response
- NAb positive subjects, that is subjects who were positive in the NAb assay at any time point analyzed.
- Maximum post-baseline titer level in treatment-emergent or treatment boosted ADA positive subjects:
 - High,
 - Moderate,
 - Low

5.11. Analysis of Biomarker Data

All biomarker analyses will be performed on the mFAS and FAS-maintenance using all observed data. Descriptive statistics for the observed values, change from baseline and percent change from baseline values by treatment and visit will be provided for the biomarker variables as described in Section 4.9.

The Wilcoxon signed-rank test will be used to test if the change or percentage change from baseline value is significantly different from zero. P-value will be reported.

For up-dosing period, exploratory analyses for the difference between dupilumab + AR101 group and placebo + AR101 group on the change from baseline and percent change from baseline values will be performed using a rank-based ANCOVA model with treatment group and randomization stratification factors as fixed factors, and the relevant baseline values as covariate. Missing value will be imputed by LOCF method using available post-baseline data for visits up to visit 16. Pvalue for difference between dupilumab +AR101 and placebo + AR101 will be provided.

For maintenance period, exploratory analyses for the difference between continuously on dupilumab + AR101 group and continuously on placebo + AR101 group on the change from baseline and percent change from baseline values will be performed using a rank-based ANCOVA model with treatment group and randomization stratification factors as fixed factors, and the relevant baseline values as covariate. Missing value will be imputed by LOCF method using available post-baseline data for visits up to visit 22. P-value for difference between continuously on dupilumab + AR101 and continuously on placebo + AR101 will be provided.

Correlation of baseline serum peanut sIgE, sIgG, sIgG4, total IgE, absolute change or percent change at visit 16, 22 and 25 from baseline in these biomarkers; baseline Ara h1 sIgE, Ara h1 sIgG4, Ara h2 sIgE, Ara h2 sIgG4, Ara h3 sIgE, Ara h3 sIgG4, absolute change or percent change at visit 16 in these biomarkers; baseline in basophil sensitivity to peanut allergen stimulation measured by EC50, frequency of peanut specific T-cell subsets (e.g. Th2A cells), and absolute change or percent change at visit 16 in these biomarkers with the following continuous clinical endpoints will be explored using the Spearman's rho test. Both Spearman correlation coefficients and p-value will be reported. The correlation between post-baseline biomarkers and clinical outcomes will only be evaluated at the same visit.

- Change in the cumulative tolerated dose (log transformed) of peanut protein during a DBPCFC from baseline to visit 16 in subjects treated with dupilumab plus AR101 vs placebo plus AR101
- Change in the cumulative tolerated dose (log transformed) of peanut protein during a DBPCFC from baseline to visit 22 in subjects (continuously) treated with dupilumab plus AR101 vs placebo plus AR101
- Change in the cumulative tolerated dose (log transformed) of peanut protein during a DBPCFC from baseline to visit 25 in subjects (continuously) treated with dupilumab plus AR101 vs placebo plus AR101
- Change in the normalized wheal size of titrated skin prick test from baseline to visit 16 in subjects treated with dupilumab plus AR101 vs placebo plus AR101
- Change in the normalized wheal size of titrated skin prick test from baseline to visit 22 in subjects (continuously) treated with dupilumab plus AR101 vs placebo plus AR101
- Change in the normalized wheal size of titrated skin prick test from baseline to visit 25 in subjects (continuously) treated with dupilumab plus AR101 vs placebo plus AR101
- Change in the FeNO from baseline to visit 16 in subjects treated with dupilumab plus AR101 vs placebo plus AR101
- Change in the FeNO from baseline to visit 22 in subjects (continuously) treated with dupilumab plus AR101 vs placebo plus AR101
- Change in the FeNO from baseline to visit 25 in subjects (continuously) treated with dupilumab plus AR101 vs placebo plus AR101

Correlation of baseline serum peanut sIgE, sIgG, sIgG4, total IgE, basophil sensitivity to peanut allergen stimulation, and Th2A cell frequency with the following binary clinical endpoints will also be explored using logistic model. The model will include the responder/non-responder of below clinical endpoint as the dependent variable, with randomization stratification factors, treatment group, baseline biomarker value, and treatment by baseline biomarker interaction as the predictor variables. Model coefficients and P-value will be provided to indicate significance of the correlation/association.

• Subjects treated with dupilumab plus AR101 vs placebo plus AR101 who "pass" 2044 mg (cumulative) peanut protein at visit 16

- Subjects treated with dupilumab plus AR101 vs placebo plus AR101 who "pass" 1044 mg (cumulative) peanut protein at visit 16
- Subjects treated with dupilumab plus AR101 vs placebo plus AR101 who "pass" 444 mg (cumulative) peanut protein at visit 16

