2. INVESTIGATION PLAN

2.1. Study Design and Randomization

This is a Phase 2, multicenter, randomized, double-blind, parallel-group, 2-arm study in subjects aged 6 to 17 years inclusive who are allergic to peanut. The study consists of a screening period of up to 16 weeks, a 28 to 40-week double-blind treatment period, a 24-week maintenance phase, and a 12-week post-treatment follow-up period. In protocol amendment 3 to accommodate COVID-19 restrictions, double-blind treatment period was extended from 28 weeks to up to 40 weeks. Subjects who attend optional visits between week 28 and week 40 will have increased duration of exposure to AR101 and dupilumab.

Approximately 156 subjects will be randomized at baseline in a 2:1 ratio into one of 2 treatment arms (n=104 to dupilumab and 52 to placebo, in combination with up-dosing of AR101) according to a central randomization scheme provided by an IWRS. Randomization will be stratified by screening peanut-specific IgE level ($\leq 100 \text{ kUA/L}$ or $\geq 100 \text{ kUA/L}$) and body weight ($\leq 30 \text{ kg}, \geq 30 \text{ kg}$ and $\leq 60 \text{ kg}$, or $\geq 60 \text{ kg}$) at randomization. A minimum of 15 subjects for each weight group will be enrolled.

At visit 16 (or at the early termination visit for those who discontinue from study prior to visit 16), subjects previously in the dupilumab plus AR101 arm will be re-randomized in a 1:1 ratio into one of 2 treatment arms (dupilumab versus placebo, in combination with AR101), according to a central randomization scheme provided by IWRS. Randomization will be stratified by whether subjects achieve 300 mg/day AR101 for at least 2 weeks by visit 16 (Yes or No).

Subjects previously in the placebo plus AR101 arm will continue their treatment of placebo plus AR101 in the maintenance phase if they achieve 300 mg/day AR101 for at least 2 weeks at visit 16.

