2.2. Statistical Hypothesis

The primary efficacy endpoint is the proportion of subjects who achieve a cumulative dose of 2044 mg peanut protein during a post up-dosing DBPCFC at visit 16. The comparison between the dupilumab + AR101 arm and the placebo + AR101 arm will be made.

Let p_D and p_P be the true proportions of subjects who achieve a cumulative dose of 2044 mg of peanut protein during a post up-dosing DBPCFC at visit 16 in the treatment arms of dupilumab + AR101 and placebo + AR101, respectively. The following hypothesis for the superiority testing will be tested at the 5% 2-sided significance level for the up-dosing phase:

H0: $p_D = p_P$, i.e., the proportion of subjects who achieve a cumulative dose of 2044 mg peanut

protein during a DBPCFC at visit 16 is the same between dupilumab + AR101 arm and the placebo + AR101 arm

against the alternative

Ha: $p_D \neq p_P$, i.e., the proportion of subjects who achieve a cumulative dose of 2044 mg peanut protein during a DBPCFC at visit 16 are different between the dupilumab + AR101 arm and the placebo + AR101 arm

CONFIDENTIAL

Page 13 of 86

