2.3. Sample Size and Power Considerations

It is assumed that the proportion of subjects who achieve a cumulative dose of 2044 mg of peanut protein during a post up-dosing DBPCFC at visit 16 in placebo plus AR101 arm will be 40%, based on an Aimmune presentation at the 2018 American Academy of Allergy, Asthma & Immunology–World Allergy Organization Joint Congress; with the proportion of subjects in dupilumab plus AR101 arm assumed to be 65%, which is considered to be clinical meaningful benefit by adding on dupilumab treatment. A sample size of approximately 156 subjects (104 in dupilumab plus AR101 and 52 in placebo plus AR101) will have 80% power to detect the treatment difference of 25% between placebo plus AR101 and dupilumab plus AR101 at the 2-sided 5% significance level (the minimum significant difference is approximately 17.8%). The sample size calculations were done by Fisher exact test using nQuery (7.0).

[figure not shown]
Approximately 122 subjects who undergo the post up-dosing DBPCFC at Week 28 (visit 16 with a window of -7/+30 days) as per protocol or discontinue from study prior to Week 28 (visit 16 with a window of -7/+30 days) will be included in the primary efficacy analysis. These subjects receive AR101 dose escalation per the original protocol's 24-week up-dosing schedule. The minimum significant difference with approximately 122 subjects is approximately 20.7% between placebo plus AR101 and dupilumab plus AR101 assuming placebo plus AR101 treatment effect is 40% at the 2-sided Fisher exact test with 5% significance level.

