4.5.3. Exploratory Efficacy Variable (s)

Exploratory efficacy endpoints include:

- Proportion of subjects who "pass" an end of study DBPCFC with 2044 mg (cumulative) peanut protein at visit 25
- Change from baseline in total FAQLQ score at visit 16, visit 22, and visit 25 for different types of FAQLQ form
- Proportion of subjects experiencing none, mild, moderate, severe or higher allergic symptoms by treatment group during DBPCFCs of peanut protein at visit 16 and visit 22
- Change and percent change from baseline to visit 16, visit 22 and visit 25 in peanutspecific IgG
- Change and percent change from baseline to visit 16, visit 22 and visit 25 in peanutspecific IgG4
- Change and percent change from baseline to visit 16, visit 22 and visit 25 in total IgE
- Change from baseline to visit 16, visit 22 and visit 25 in log- transformed peanut-specific IgG4/ peanut-specific IgE ratio
- Change from baseline to visit 16, visit 22 and visit 25 in log- transformed peanut-specific IgG/ peanut-specific IgE ratio
- Change from baseline to visit 16, visit 22 and visit 25 in peanut-specific IgE
- Change from baseline to visit 16, visit 22 and visit 25 in log- transformed peanutspecific IgE/total IgE ratio
- Change and percent change from baseline to visit 16, visit 22 and visit 25 in Ara h1 sIgE, Ara h1 sIgG4, Ara h2 sIgE, Ara h2 sIgG4, Ara h3 sIgE, Ara h3 sIgG4
- Change from baseline to visit 16, visit 22 and visit 25 in log- transformed Ara h1-specific IgG4/ Ara h1-specific IgE ratio
- Change from baseline to visit 16, visit 22 and visit 25 in log- transformed Ara h2-specific IgG4/ Ara h2-specific IgE ratio
- Change from baseline to visit 16, visit 22 and visit 25 in log- transformed Ara h3-specific IgG4/ Ara h3-specific IgE ratio

- Change from baseline to visit 16, visit 22 and visit 25 in Ara h1-specific IgE/ peanutspecific IgE ratio
- Change from baseline to visit 16, visit 22 and visit 25 in Ara h2-specific IgE/ peanut-specific IgE ratio
- Change from baseline to visit 16, visit 22 and visit 25 in Ara h3-specific IgE/ peanut-specific IgE ratio
- Change and percent change from baseline to visit 16, visit 22 and visit 25 in basophil sensitivity to peanut allergen, as measured by EC50, which is the concentration of peanut protein required to achieve 50% of maximal basophil activation
- Change and percent change from baseline to visit 16, visit 22 and visit 25 in the frequency of peanut-specific T cell subsets (e.g. Th2A cell)

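### SAP 5.11 applies the signed-rank test to percentage change in biomarkers, a scale that is skewed even when nothing has changed, so these within-arm p-values are miscalibrated (minor)

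*SAP*

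**What the plan says.** SAP 5.11 (Analysis of Biomarker Data) sets a one-sample test within each arm: "The Wilcoxon signed-rank test will be used to test if the change or percentage change from baseline value is significantly different from zero". A p-value is to be reported. The section gives no transformation, no check of symmetry, no significance level and no multiplicity rule for this test.

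The data are defined in the same section: "All biomarker analyses will be performed on the mFAS and FAS-maintenance using all observed data".

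Percentage change is a planned scale for many markers. SAP 4.5.3 lists, for example, "Change and percent change from baseline to visit 16, visit 22 and visit 25 in total IgE". It does the same for peanut-specific IgG and IgG4, the Ara h1 to h3 antibodies, basophil EC50 and T-cell subset frequency. SAP 4.9, to which 5.11 refers, adds peanut-specific IgE and FeNO. SAP 4.5.3 puts several antibody ratios on the log scale, but not the percentage changes.

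Between-arm biomarker comparisons in 5.11 use a rank-based ANCOVA and are labelled exploratory. Formal error control (SAP 5.6.3) covers only the primary and first secondary endpoints.

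**The concern.** The null distribution of the signed-rank statistic holds only if positive and negative values of the same size are equally likely. If baseline and follow-up are exchangeable, this is true of the absolute change and of the log ratio. It is not true of 100 x (follow-up - baseline)/baseline. A doubling scores +100% and a halving scores -50%, so rises take the larger ranks and the test responds to skewness as if it were an increase.

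Three consequences follow:

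- A marker that has not moved may be reported as significantly raised.
- A moderate true fall may be missed. Protocol section 1 hypothesises a fall in peanut-specific IgE.
- The change and percentage-change p-values from the same data may disagree, and the SAP does not say which one governs.

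**Working it through.** **The plan's own figures.** The documents give no operating characteristic for this test. The only stated power is 80% for the primary endpoint (104 against 52, 65% against 40%, Fisher exact test, SAP 2.3). Exact enumeration gives 81.1%, so that figure reproduces.

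**Inputs from the documents**
- Randomisation: "Approximately 156 subjects will be randomized at baseline in a 2:1 ratio into one of 2 treatment arms". SAP 2.1 sets the planned arm sizes at 104 for dupilumab and 52 for placebo.
- Analysis set: "Approximately 122 subjects who undergo the post up-dosing DBPCFC at Week 28", or who discontinue earlier, enter the primary analysis. If the mFAS keeps the 2:1 ratio, that is 122 x 2/3 = 81 on dupilumab and 122/3 = 41 on placebo. Observed data only may give fewer.
- Maintenance: "subjects previously in the dupilumab plus AR101 arm will be re-randomized in a 1:1 ratio into one of 2 treatment arms". Each dupilumab subgroup therefore has at most 104/2 = 52 subjects at visits 22 and 25.

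**Assumptions**
- Level: 5% two-sided. SAP 2.2 states this for the primary hypothesis only.
- SD of the log ratio L = ln(follow-up/baseline): not in the documents, so varied from 0.2 to 1.3.
- No change: L is normal with mean 0, so the median ratio is 1.

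**Mechanism in six values.** Take ratios 1.5, 2 and 3 and their reciprocals, which are perfectly balanced. The percentage changes are +50, +100, +200 and -33, -50, -67. Ranked by size, the rises get 2.5 + 5 + 6 = 13.5 and the falls 1 + 2.5 + 4 = 7.5. Under symmetry each sum would be 10.5. On the log scale both are 10.5.

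**Test.** z = (W+ - n(n+1)/4) / sqrt(n(n+1)(2n+1)/24), where W+ is the rank sum of the positive values. For n = 81 the mean is 81 x 82/4 = 1660.5 and the SD is sqrt(81 x 82 x 163/24) = 212.4.

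**Rejection rate with no change** (percentage change, 20,000 simulated samples per cell)

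| SD of log ratio | n = 41 | n = 52 | n = 81 |
|---|---|---|---|
| 0.2 | 6% | 6% | 7% |
| 0.3 | 7% | 8% | 9% |
| 0.5 | 10% | 12% | 16% |
| 0.7 | 14% | 17% | 25% |
| 1.0 | 20% | 25% | 37% |
| 1.3 | 27% | 33% | 48% |

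Repeat runs at n = 81 gave 9% to 10% at SD 0.3 and 47% to 50% at SD 1.3. Most of the excess is false rises. At n = 81 and SD 0.5, rises are 15.9% and falls 0.2%, against 2.5% each for a correct test. The log-ratio test stays near 5% in every cell, and the test on absolute change gives 4.6% to 5.3% under exchangeability.

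**Sensitivity at n = 81**
- Heavier-tailed (Laplace) log ratio: about 10% at SD 0.5 and 21% at SD 1.0.
- No change defined as zero mean percentage change (L has mean -SD²/2): the error reverses, with about 21% false falls at SD 0.5.

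**Power to detect a true median fall at n = 81**

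| Fall | SD | Percentage change | Log ratio |
|---|---|---|---|
| 20% | 0.7 | 30% | 79% |
| 30% | 1.0 | 27% | 87% |
| 50% | 0.7 | about 100% | about 100% |
| 50% | 1.0 | 97% | about 100% |
| 50% | 1.3 | 66% | about 100% |

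For a 50% fall at n = 41, percentage change has about 80% power at SD 1.0 and 40% at SD 1.3.

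**The case against.** The strongest reply is that nothing important rests on this test. That largely stands. It is a one-sample, within-arm p-value. The between-arm rank-based ANCOVA is unaffected, because percentage change is an increasing function of the ratio, so ranks across subjects are the same on either scale, and no symmetry about zero is needed. The secondary endpoint of percentage change in peanut-specific IgE is also analysed by rank-based ANCOVA (SAP 5.6.2). Protocol 5.6 says basophil results will not appear in the study report, so part of the affected output may never be published.

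Three stronger readings are tempting, and the documents support none of them.

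- **A false-positive rate of 16% to 50% as a general figure.** This needs an SD of roughly 0.5 to 1.3 with 81 subjects. The documents give no SD, the rate is 7% to 10% at SD 0.2 to 0.3, and 81 applies only up to visit 16.
- **The expected IgE effect would be hidden.** Protocol 5.6 cites total IgE suppression of about 50% within 12 to 16 weeks, which the test still finds unless the SD is high. The same section cites IgG4 rises of 3.5-fold and about 10-fold during immunotherapy, so no change is not the expected case for that marker.
- **The treatment comparison is biased.** False rises are more frequent in the larger arm (16% against 10% at SD 0.5). This misleads only a reader who compares within-arm p-values instead of using the planned between-arm test.

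The reply does not restore the p-value. It is miscalibrated whether no change means a median ratio of 1 or a mean percentage change of zero; only the direction of the error differs. The no-change case is also plausible for some results. Protocol 5.6 cites peanut-specific IgE returning to baseline after a year of immunotherapy, close to visit 22.

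**Conclusion.** The point holds, as a minor one. Followed exactly, SAP 5.11 gives miscalibrated within-arm p-values for percentage change. With a median ratio of 1 and a normal log ratio of SD 0.2 to 1.3, the two-sided 5% test rejects in about 7% to 50% of cases at n = 81 and about 6% to 33% at n = 41 to 52, almost always as a rise at all but the smallest SDs. Heavier tails give lower rates. Falls of 20% to 30% are detected with about 27% to 30% power where the log ratio would give about 79% to 87% (n = 81, SD 0.7 to 1.0).

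The mechanism is certain. The size rests on an SD that the documents do not supply, and the direction rests on what is meant by no change. The effect is confined to exploratory within-arm p-values. These include any such p-value for peanut-specific IgE, but not the analysis of that secondary endpoint.

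**What to change.** In SAP 5.11:

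- Apply the signed-rank test to the log ratio (log follow-up minus log baseline).
- Report the estimate as a back-transformed ratio (geometric mean or Hodges-Lehmann), expressed as a percentage.
- Keep percentage change as a descriptive summary with no signed-rank p-value of its own.

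The cost is one sentence of SAP text and a small programming change before database lock, with no new data. The log scale is already used for the antibody ratios in SAP 4.5.3. SAP 6.2 replaces values below the quantification limit with half that limit, so their logs exist. A short rule for true zeros, such as a T-cell frequency of zero, would complete the text.

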5.6. Pharmacodynamic and Biomarker Variables

Pharmacodynamic and biomarker variables are:

Serum Total IgE: Serum total IgE is a marker of Type 2 activity. Dupilumab significantly suppressed total IgE in studies of adult AD, nasal polyposis, and asthma patients.

Serum Peanut-Specific Antibody Assays (IgE, IgG, IgG4 against peanut extract and peanut protein allergen components): The induction of peanut allergen specific IgG4 during OIT has been reported in multiple studies. In a 5-year peanut OIT study of 39 peanut-allergic children, increases in total peanut-specific IgG levels were reported during the 12-month up-dosing period (Vickery 2014). In an open-label study of 29 peanut-allergic children, peanut-specific IgG4 increased steadily during the first year of treatment, reaching 3.5-fold increase over baseline after 3 months of OIT and roughly 10-fold increase at the end of first year (Jones 2009). In the same study, peanut allergen specific IgE was seen to increase by ~3-fold after 3 months of OIT and gradually return to baseline at one year.

In study R668-AD-1307 and other dupilumab studies in adults, dupilumab suppressed both total and allergen-specific IgEs. In general, dupilumab suppresses total IgE by \sim 50% with 12 to 16 weeks of treatment.

Regeneron Pharmaceuticals, Inc.

CONFIDENTIAL

Page 42 of 118

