1.2.2. Secondary Objectives

- To assess whether dupilumab as adjunct to AR101 compared to placebo as adjunct to AR101 improves desensitization at the completion of up-dosing, defined as an increase in the cumulative tolerated dose (log transformed) of peanut protein during a post up-dosing DBPCFC at visit 16
- To assess whether dupilumab as (indefinite [continuously]) adjunct to AR101 compared to placebo maintains desensitization, defined as an increase in the proportion of subjects who pass a post maintenance DBPCFC at visit 22
- To assess whether dupilumab as (limited [previously]) adjunct to AR101 compared to placebo maintains desensitization, defined as an increase in the proportion of subjects who pass a post maintenance DBPCFC at visit 22
- To evaluate the safety and tolerability of dupilumab as adjunct to AR101 compared to placebo
- To assess the effect of dupilumab (compared to placebo) as adjunct to AR101 on the change in peanut-specific IgE, IgG, IgG4, peanut-specific IgG4/IgE ratio, and peanut-specific IgG/IgE ratio

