5.6.4. Analysis of Exploratory Efficacy Variables

The analysis of other efficacy variables will be the same as the primary analysis described in Section 5.6.1 and Section 5.6.2 with the following exceptions. The analysis on biomarker variables will be specified in Section 5.11. The analysis on the proportion of days with allergy symptoms based on eDiary data will be specified in Section 5.12.

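### For most visit 25 biomarkers, and for the dupilumab-then-placebo arm, SAP 5.11 tests change from baseline only against zero, which cannot isolate a dupilumab effect; on percent change that test also over-rejects

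*SAP*

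**What the plan says.** SAP 5.6.4 takes biomarkers out of the general efficacy methods: "The analysis on biomarker variables will be specified in Section 5.11". Section 5.11 then provides, on the mFAS and FAS-maintenance:

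- descriptive statistics by treatment and visit;
- a one-sample test with a reported p-value: "The Wilcoxon signed-rank test will be used to test if the change or percentage change from baseline value is significantly different from zero";
- a rank-based ANCOVA for up-dosing: "Pvalue for difference between dupilumab +AR101 and placebo + AR101 will be provided";
- a rank-based ANCOVA for maintenance, limited to "exploratory analyses for the difference between continuously on dupilumab + AR101 group and continuously on placebo + AR101 group", with the data range set by "Missing value will be imputed by LOCF method using available post-baseline data for visits up to visit 22";
- Spearman correlations and logistic models relating biomarkers to clinical outcomes.

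SAP 4.5.3 lists visit 25 endpoints for many markers, for example "Change and percent change from baseline to visit 16, visit 22 and visit 25 in total IgE". It does the same for peanut-specific IgG and IgG4, absolute change in peanut-specific IgE, the antibody ratios, the Ara h components, basophil EC50 and T-cell subsets. The one biomarker with a between-arm analysis at visit 25 is percent change in peanut-specific IgE, continuous dupilumab versus placebo (SAP 5.6.2 and 10.1).

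The related secondary objective in SAP 1.2.2 is comparative: "To assess the effect of dupilumab (compared to placebo) as adjunct to AR101 on the change in peanut-specific IgE, IgG, IgG4".

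**The concern.** A p-value against zero asks whether a marker moved. The objective asks whether it moved differently on dupilumab than on placebo. All arms take AR101 through up-dosing and maintenance, and the protocol itself expects oral immunotherapy to move at least one of these markers strongly: "peanut-specific IgG4 increased steadily during the first year of treatment, reaching 3.5-fold increase over baseline after 3 months of OIT" (Protocol 5.6).

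The missing comparisons fall where persistence would show. Protocol 3.2.2 says re-randomisation is there to assess a lasting or limited effect of dupilumab. Visit 25 and the switched arm carry that question, and the SAP does compare the switched arm with placebo on the visit 22 food challenge (4.5.2, 5.6.2). With only one-sample p-values in the biomarker tables, a reader may take significance in one arm and not in another as evidence of a difference between arms.

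A separate problem concerns scale. The signed-rank test assumes that changes are symmetric about zero when nothing has happened, and percent change in a positive marker is not: a doubling is +100% but a halving is −50%.

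**Working it through.** **1. Coverage of tests of change from baseline.** Reading SAP 5.6.2, 5.6.4, 5.11 and 10.1 together:

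| Comparison | Between-arm test? |
|---|---|
| Dupilumab vs placebo, to visit 16 | Yes, 5.11 |
| Continuous dupilumab vs continuous placebo, to visit 22 | Yes, 5.11 |
| Same arms, visit 25, percent change in peanut IgE | Yes, 5.6.2 |
| Same arms, visit 25, all other biomarkers | No |
| Dupilumab-then-placebo vs any arm, visits 22 and 25 | No |

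**2. What the one-sample test shows when dupilumab does nothing.** The plan states no power or error rate for biomarkers, so there is no figure to reproduce. Arm sizes: 104 / 2 = 52 per re-randomised arm and 52 on placebo; with the roughly 20% up-dosing failure quoted in Protocol 1, 52 × 0.8 ≈ 42; 31 is a lower case. Assumptions: normal change with the same mean shift in both arms, 1,500 runs per setting, two-sided 5%. The ANCOVA used ranks of change and baseline, without stratification factors. Writing a and c for the two signed-rank rejection rates, the chance that exactly one independent arm is significant is a(1 − c) + c(1 − a).

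| Shared shift | n per arm | Signed-rank, switched arm | Signed-rank, placebo arm | Exactly one significant | Rank ANCOVA |
|---|---|---|---|---|---|
| 0.3 SD | 31 | 33% | 37% | 46% | 6% |
| 0.3 SD | 42 | 48% | 48% | 50% | 5% |
| 0.3 SD | 52 | 55% | 55% | 49% | 5% |
| 0.5 SD | 31 | 73% | 74% | 39% | 5% |
| 0.5 SD | 42 | 87% | 89% | 21% | 5% |
| 0.5 SD | 52 | 93% | 95% | 11% | 5% |
| 1.0 SD | 31 to 52 | about 100% | about 100% | about 0% | 4% to 5% |

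For scale, the protocol's 3.5-fold IgG4 rise is ln 3.5 = 1.25 on the log scale. With an SD of log ratio between 0.5 and 1.0 that is 2.5 to 1.25 SD, beyond the last row. This applies to IgG4 during ongoing immunotherapy.

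**3. Percent change with no true change.** Let L be the log ratio to baseline, normal with mean 0. Percent change is 100(e^L − 1). Its median is zero, but its positive values are larger in size than its negative ones and so take the higher ranks. Rejection at 5% (10,000 runs each):

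| SD of L | n = 30 | n = 42 | Same test on L |
|---|---|---|---|
| 0.3 | 7% | 8% | 5% |
| 0.5 | 8% | 10% | 5% |
| 0.8 | 13% | 17% | 5% |
| 1.0 | 16% | 21% | 5% |

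Absolute change between exchangeable log-normal values before and after treatment is symmetric about zero, and the test keeps its level (about 5%). The IgG4/IgE and IgG/IgE ratios are already log-transformed in SAP 4.5.3. The between-arm rank ANCOVA is unaffected, because percent change rises strictly with L and gives the same ranks across subjects.

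**The case against.** The strongest reply is that the plan declares this territory descriptive. SAP 1 promises descriptive summaries for maintenance and follow-up, with inference for maintenance only if needed. Protocol 11.4.3.2 treats visit 22 and 25 secondary endpoints descriptively, Protocol 11.4.7 does the same for exploratory biomarkers, and SAP 5.6.3 has no formal hypothesis for maintenance. The comparative objective names no visit, and it does have between-arm tests at visits 16 and 22. All of this stands and limits the weight of the point. It does not remove it, because 5.11 still reports p-values at these visits, and they do not bear on dupilumab versus placebo.

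Four stronger readings are tempting and are not supported:

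- A reader might infer that the SAP passes off the signed-rank result as a dupilumab effect. It never says so. It does not even state that the test is run by arm; that follows only from the preceding sentence on summaries by treatment and visit.
- A reader might infer that every marker will be significant in every arm because of AR101. The large rise cited is for IgG4 during treatment. Protocol 5.6 has peanut-specific IgE back near baseline at one year and gives no immunotherapy shift for total IgE. Visit 25 comes 12 weeks after peanut and dupilumab stop, and the test absorbs all sources of change.
- A reader might infer that no other p-value uses visit 25 biomarkers. The Spearman correlations do, but they test association with clinical outcomes.
- A reader might infer that dupilumab-then-placebo versus placebo is a fully randomised contrast. FAS-maintenance requires 300 mg/day for at least 2 weeks (SAP 3.1), an outcome that follows randomisation.

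Basophil and Th2A tests are optional, so their arm sizes may be smaller than those used here. Protocol 5.6 also keeps the basophil results out of the study report.

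**Conclusion.** The point holds as a gap in an exploratory analysis. For the visit 25 biomarkers other than percent change in peanut-specific IgE, and for the dupilumab-then-placebo arm at visits 22 and 25, the only planned test of change from baseline is against zero. With no dupilumab effect that test rejects anywhere from 33% to 100% of the time for shared shifts of 0.3 to 1.0 SD, while the between-arm model stays at about 5%.

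Separately, the version on percent change rejects about 8% to 21% of the time when nothing has changed, for SD of log ratio 0.5 to 1.0 and 30 or 42 per arm, and 7% to 8% at SD 0.3. The absolute-change and log-ratio versions do not share this fault.

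The documents give no SDs and no visit 25 values, so the shifts, SDs and distributions are assumptions. The structural gap does not depend on them. The primary endpoint and the first secondary endpoint are untouched.

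**What to change.** In SAP 5.11:

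1. Extend the rank-based ANCOVA already specified (treatment, stratification factors, baseline value) to visit 25.
2. Add two exploratory contrasts at visits 22 and 25: dupilumab-then-placebo versus continuous placebo, stating that FAS-maintenance is conditioned on reaching 300 mg/day and so randomisation does not fully protect it; and continued versus switched dupilumab, which is the re-randomised contrast and was stratified on reaching 300 mg/day (SAP 2.1).
3. State that the signed-rank test is run within arm, label its p-values as describing change on AR101-containing treatment and not a dupilumab effect, and compute them on the log ratio to baseline instead of percent change.

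The cost is a few sentences and some extra table columns. No new data or visits are needed. The downside is a few more exploratory p-values; the alpha-controlled tests are unaffected.
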